3.4.3. Other outcomes

3.4.3.a. Other UUI/OAB outcomes

i. Bladder diary – We will assess the change in IE frequency and type, number of urgency episodes, urgency severity with voids, number of diurnal voids, and number of nocturnal voids and compare these variables between groups at 6 months and 1 year.

ii. Overactive Bladder treatment satisfaction (OAB-SAT-q)⁵⁸-The OAB-SAT-q is an 11 item instrument designed to assess patient satisfaction with treatment in a clinical setting. There are three 3-item subscales (Satisfaction, Side Effects, Endorsement) and two single items (Convenience, Preference). Response options are presented on 4-, 5-, and 6-point Likert scales. It has demonstrated good psychometric properties in OAB/UUI patients receiving anticholinergic and anticholinergic + behavioral therapies. We will compare change from baseline in OAB-SAT-q scores at 6 months and 1 year between treatment groups.

iii. Overactive Bladder Questionnaire-Symptom subscale (OAB-q) – The OAB-q is a validated, responsive questionnaire that includes 8 symptom bother items (SS) and 25 health related quality of life (HRQOL) items of 4 subscales (coping, concern, sleep, and social interaction).⁵⁵ In a systematic review of UI questionnaires by Avery et al, the OAB-q was rated as “grade A”, highest recommendation specifically for OAB symptoms.⁵⁹ Each item is rated on a 6-point Likert scale ranging from “not at all bothered” to “a very great deal bothered” for symptom items and “none of the time” to “all of the time” for HRQOL items. Subscales are summed and transformed into scores ranging from 0-100 with higher bother scores indicating increasing symptom bother and higher HRQOL scores indicating better quality of life.^{60,61} We will compare change from baseline in OAB-q scores at 6 months and 1 year between treatment groups.

3.4.3.b. Time to failure

For analyzing time to failure, “failure” will be defined as initiation of any additional treatment for either SUI or UUI/OAB symptoms during the follow-up period. Subjects lost to follow up will be censored at the time of their last visit.

3.4.3.c. Quality of life/global impression

We will compare change from baseline in the scores below at 6 months and 1 year between treatment groups.

- a) Incontinence Impact Questionnaire (IIQ)
- b) Pelvic Organ Prolapse/Urinary Incontinence Sexual Questionnaire (PISQ)⁶²
- c) European Quality of Life-5 Dimensions (EQ-5D)⁶³
- d) Adaptation Index
- e) Patient Global Impression of Improvement (PGI-I)³ and Patient Global Impression of Severity (PGI-S)³:

3.4.3.d. Safety/additional treatment

- a) additional re-treatments for SUI or UUI within 12 months of treatment, and type of re-treatment
- b) return to OR for sling revision due to worsened OAB symptoms

3.4.3.e. Pelvic floor muscle (PFM) strength

PFM strength has traditionally been measured subjectively by a clinician or interventionist using the Brink score in many previous studies, including Network studies. However, because this is a subjective measure, it may be subject to bias. Although there are many trials showing symptom improvement with pelvic floor therapy²⁰, there are limited studies evaluating the association between PFM *strength* and improvements in UI symptoms. To contribute to the literature about this issue, in ESTEEM we will objectively assess PFM strength changes using the Peritron Perineometer. Peritron is an advanced pressure biofeedback perineometer specifically designed for pelvic floor assessment. Pelvic floor muscle contraction creates pressure in the sensor that is transferred and displayed on a “Readout Unit” which is small and handheld.

FIGURE 4. Peritron Perineometer

Example: Peritron 9300 Device (www.win-health.com/perineometer.html)

After a thorough search of the literature and discussion with other experts in the field, the protocol investigators concluded that the Peritron device has adequate evidence to support its validity, including test-retest reliability and inter-rater reliability, for both baseline and maximum contraction pressure measurements. In addition, studies support its reliability in “normal”, continent controls as well as women with UI.

Studies evaluating the Peritron’s reliability properties are in Table 4. A study by Hundley et al supports the reliability of measurements from this device in postmenopausal, parous women (inter-rater reliability for baseline and maximum pressure 0.78 to 0.88).⁶⁴ This is supported in normative women as well (correlation $r=0.83$).⁶⁵ The Peritron device provides a potential method of determining an objective measure of PFM strength. Measurement using the Peritron device will be standardized and Principal Investigators at each site will be trained on how to use the device and will be responsible for training their clinical staff and for quality assurance of Peritron use. Clinical staff performing the Peritron measurements will be masked to the intervention the subject received. PFM measures (Maximum squeeze amplitude and duration of squeeze), will be performed at baseline, at the first post-operative visit after surgery (2 weeks), 8 weeks, and at the primary endpoint (12 months) – See Assessment Table 11. Changes in squeeze measures from baseline at 8 weeks and 12 months will be compared between treatment groups.

Table 4. Validity properties of Peritron device

Author (year)	N	Subject characteristics	Study aims	Peritron Findings
Kersch-Schindal et al (2002) ⁶⁶	37	Postmenopausal all with UI (28 SUI; 5 UUI; 4 MUI)	1. To examine the test-retest reliability of several PFM measures. 2. To correlate findings between different measures.	Peritron Reliability: -ICC for max contraction = 0.97 -ICC for mean contraction over 5 seconds = 0.95 -Correlation between max force and mean contraction force over 5s = $r = 0.95$. Correlations with other measures: - urine stop test $r = 0.88$ max force - digital exam $r = 0.70$ max force - pad tests $r = -0.33$ and -0.28 for max
Hundley et al (2005) ⁶⁴	100	Mean age 48 (22 to 85) yrs 46% postmenopausal	1.To compare Brink scores with Peritron measurement 2. Determine intra- and inter-rater reliability for the Peritron.	Peritron Reliability: -Interrater reliability max pressure, $r = 0.88$ Brink Reliability: -Interrater Brink for total score = 0.68, pressure = 0.68, vertical displacement = 0.58, and squeeze duration = 0.44 Correlations with other measures: - Brink pressure $r = 0.67$
Bo et al, 2005 ⁶⁵	20	“Normals” PT students Mean age 25.1 (21-38) yrs.	To assess whether max vaginal squeeze pressure differed when measured with 2 different sized probes.	Peritron Reliability: Test-retest: $r^2 = 0.83$
Frawley et al (2006) ⁶⁷	20	19 female PT (1 unable to contract) Age range 25-65 yrs Some parous subjects reported mild UI and/or prolapse	1. To determine the intra-therapist reliability for digital muscle testing and vaginal manometry on max voluntary contraction and endurance. 2. To establish how reliability varied with different tools and different testing positions.	Peritron Reliability: -Test-retest for Max pressure: $r = 0.91$ to 0.96 across positions (supine lowest at 0.91). -pressure endurance $r = 0.05$ to 0.41 with hooklying the lowest
Rahmani et al (2009) ⁶⁸	15	20-50 yrs	1. Test-retest reliability	Peritron Reliability: -Test-retest (same day) Max pressure: ICC=.95 -Test-retest (same day) Endurance: ICC=.94 -Test-retest (between-days) Max pressure: ICC=.88 -Test-retest (between day) Endurance: ICC=.83

3.4.3.f. Cost-effectiveness outcomes

The cost-effectiveness analysis will be conducted from a societal perspective and will be expressed as incremental cost required to produce one additional unit of quality-adjusted life year (QALY). Data on each subject’s use of medical and non-medical resources, related to urinary incontinence will be collected during

the follow up period. Direct and indirect costs of the treatment of urinary incontinence with combined midurethral sling (MUS) and peri-operative behavioral/pelvic floor therapy (BPTx) compared to MUS alone and women’s preference for health states for improvement in urinary incontinence will be estimated.

We plan to capture incremental direct health care, direct non-medical, and indirect resource use related to study interventions and complications and other urinary incontinence management (such as other UI treatment, UI products and management of side effects). Costs will be estimated using the resource costing method. Direct medical service use collected from each study case report form and direct non-medical and indirect costs collected from patient questionnaires are monetized by multiplying the number of units of each resource use by the average unit cost of this item in dollars. Detailed individual cost data will not be collected. This method allows a consistent capture of resource use when costs are incurred across multiple health systems or payers. Detailed case report forms, that include the interventions performed (e.g. midurethral sling surgery and behavioral/pelvic floor therapy sessions) and clinical events (e.g. complications and additional treatment) will be completed by the study coordinator at study visits. Patient questionnaire on direct non-medical costs (e.g. pads, laundry) and indirect costs (e.g. time, lost productivity) will be completed at study visits 3, 6 and 12 months. Data from medical resource types (physician visits, behavioral/pelvic floor therapy sessions, medications, hospital admissions and emergency room visits) will be collected. Cost for each direct medical service use, direct non-medical items, and indirect items will be assigned based on national Medicare reimbursement rates or other standardized unit costs as indicated in the following Table 5.

Table 5: Resource utilization data collection and price data source, by utilization category

Service	Source Documentation	Price Weight
Surgery: midurethral sling	Case Report Form	Medicare reimbursement
Behavioral/pelvic floor therapy	Case Report Form	Medicare reimbursement
Medication	Case Report Form	Drug Red Book
Physician visit	Case Report Form	Medicare reimbursement
Complication: surgery	Case Report Form	Medicare reimbursement
Complication: hospitalization	Case Report Form	Medicare reimbursement
Complication: ER visit	Case Report Form	Medicare reimbursement
UI products	Questionnaire	Average national cost
UI laundry / dry cleaning	Questionnaire	Average cost
Time	Questionnaire	Average cost
Lost Productivity	Questionnaire	Average cost

Rationale for using the EQ-5D to measure Utility Values

The European Quality of Life-5 Dimensions (EQ-5D) (EuroQol Group, <http://www.euroqol.org>), preference-based utility index algorithm will be used to calculate each subject’s utility index.⁶⁹ This instrument will be collected at baseline and follow up study visits (3, 6, and 12 months). The EQ-5D has 5 attributes (mobility, self-care, usual activities, pain/discomfort and anxiety/depression) with 3 levels each for a possible 243 unique health states. The EQ-5D scoring Function is based on the time-tradeoff method with UK Scores ranging from -0.59 to 1.00 and US Scores from -0.11 to 1.00. This instrument has been previously validated in women with urinary incontinence (Penn preliminary data, Tables 6 and 7) and used in women with urinary incontinence.^{70, 71} These data will be used to compare change in QALYs between the two treatment groups. We are choosing to use a general scale to calculate change in utilities (rather than condition-specific) to allow for comparison of cost-effectiveness results with other interventions and diseases.

A questionnaire to measure direct non-medical costs (e.g. pads, laundry) and indirect costs (e.g. time, lost productivity) will be administered. Based on similar questionnaires used in SISTEr¹⁷ and ValUE⁷² studies, this instrument should take approximately 15 minutes for a subject to complete at baseline and 3, 6 and 12 months.

Table 6: Mean utility preference scores for women with urge incontinence, stress incontinence and mixed incontinence.

	UUI (n = 40)	MUI (108)	SUI (n=54)	p-value ^a
HUI-3	0.78 ± 0.23	0.79 ± 0.24	0.86 ± 0.15	0.29
EQ-5D	0.71 ± 0.23	0.73 ± 0.26	0.81 ± 0.16	0.02
SF-6D	0.76 ± 0.12	0.74 ± 0.12	0.81 ± 0.11	0.02
VAS ^b	0.78 ± 0.15	0.78 ± 0.16	0.80 ± 0.14	0.63

UUI = urge incontinence SUI = stress incontinence, MUI = mixed urge and stress incontinence

^a Kruskal Wallis ^b VAS scores were divided by 100 to enhance comparability

Table 7: Utility preference score correlations with symptom severity and condition-specific HRQOL measures

	HUI-3	EQ-5D	SF-6D	VAS
	r-value ^a	r-value ^a	r-value ^a	r-value ^a
PFDI-20 score	-0.32	-0.42	-0.37	-0.22
Bladder subscore	-0.16	-0.26	-0.24	-0.23
PFIQ-7 score	-0.45	-0.48	-0.50	-0.32
Bladder subscore	-0.29	-0.31	-0.41	-0.26

Lower scores on the HUI-3, EQ-5D, SF-6D and VAS represent worse utility values while higher scores on the PFDI, ISI and PFIQ represent worse symptom severity and quality of life. ^a Spearman correlation

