Subjects who initiate additional treatment will be asked to complete all primary and secondary outcome measures prior to initiation of additional treatment. The type of additional treatment will not be limited and will be left to the physician's clinical judgment. This may include (but is not limited to) behavioral and/or pelvic floor therapy, continence pessary, medical therapy, other procedure-based treatments (posterior tibial nerve stimulation, Botox), and surgical (sling revision, re-placement, sacral neuromodulation). Statistical models designed to specifically account for subjects who initiate additional treatment will be used. Please see Section 6, Statistical Considerations section for details on how the analysis of primary and secondary outcomes measured at 1 year will account for any additional treatment requests for SUI and/or OAB if initiated prior to the 1 year time point.

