5.5. Patient management and follow-up

5.5.1. Baseline Procedures

In addition to information collected to determine eligibility and standardized questionnaires, the following information will be obtained for all randomized patients by chart review or patient report:

- a. Demographic information: age, race, ethnicity, insurance status, education
- b. Medical history: vaginal parity, comorbidities, height, weight, prior pelvic surgeries, medications, estrogen status, previous treatments for pelvic floor disorders
- c. Social history: tobacco use
- d. Pelvic, rectal exam, neurological examination, POP-Q, PFM strength (collectively will include Brink and Peritron measurement), post-void residual, urinary stress test
- e. Standardized urodynamic evaluation (UDE) will be performed preoperatively – There continues to be controversy regarding the usefulness of UDE for preoperative evaluation of SUI. However, it is often recommended in women who have a “mixed” UI picture and there are no definitive studies to determine if UDE parameters may be helpful in predicting outcomes after surgery in women with MUI. Therefore, the protocol team agreed that patients in ESTEEM should undergo UDE testing, primarily to allow evaluation of variables that may predict clinical outcome. Because eligibility includes women electing surgery, and because this is a complex population, many patients may already have UDE results prior to enrollment. For those women who have not, they will undergo testing preoperatively, although there are no specific UDE parameters that determine eligibility for this trial. Urodynamic tests performed within the past 18 months will be allowed.
- f. Patient-reported outcomes and questionnaires – includes UDI, IIQ, EQ5D, Adaptation questionnaire, PGI-I, PGI-S, OAB-q, OAB-sat-q, PISQ,

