Amaro 2005 ¹¹⁸	SUI	N=101 Comparative cohort G1 = SUI	Max amp: G1=26.1 (1.15) G2=38.4 (1.33)		P<.001 for all 3 baseline	

		G2=controls	Mean amp: G1=15.4 (.62) G2=28.1 (1.22) Duration (s) G1=8.9 (.17) G2=11.8 (.96)		comparisons	
Gilling 2009 ¹¹⁹	SUI	N=70 RCT G1=Estim G2=Sham	Max amp: G1=17.3 (1.8) G2=15.5 (1.9)	8 wks: G1=19.2 (2) G2=15.1 (1.9)	ND	Subgroup findings: "Patients with poor initial PFM ctx by perinometer randomized to Estim had better UI outcomes than sham" but cannot tease out their PFM scores
Hung 2011 ¹²⁰	Any UI	N=23 PMT Prospective cohort, pre- post- PFM program 65% SUI 35% MUI 39% UUI	Max amp: 27 (15.0)	4 mos: 41 (24.9)	<.001	
Gamerio ¹²¹	SUI vs UUI	N=51 Cross-sectional G1=SUI (N=22) G2=UUI (N=29)	Max amp: G1=26.5 (3) G2=21.7 (.79) Mean peak G1=16.56 (1.19) G2=13.72 (0.56) Duration: G1=9.54 (0.18) G2=8.43 (.42)		P<.001 for all 3 baseline comparisons	Unclear clinical meaning

h. To determine the cost effectiveness of combined midurethral sling (MUS) and peri-operative behavioral/pelvic floor therapy (BPTx) compared to MUS alone on successful treatment of MUI symptoms

Differential mean costs and differential mean QALYs between the two treatment groups will be estimated using multiple regression analysis. Specifically, a generalized linear model with appropriate link function (e.g., log-link) and response probability distribution (e.g., gamma distribution) will be used to analyze costs due to the potential skewness and heteroscedasticity of medical expenditure data, while an ordinary least squares regression will be used for analyzing QALY data. The models will account for treatment group, study site and stratification factors, as well as other characteristics of the subjects that are found to differ significantly between the groups. When estimating QALYs, we will also adjust for subjects' baseline utility scores to account for potential imbalance in baseline utility between the two treatment groups.¹²²

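### The protocol is inconsistent on whether the cost questionnaire is taken at baseline, and the cost model pre-specifies no baseline cost term; settling both could add some precision to exploratory aim 8

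*Protocol*

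**What the plan says.** **Schedule.** Protocol 3.4.3.f describes a patient questionnaire on direct non-medical costs (pads, laundry) and indirect costs (time, lost productivity). The paragraph on resource costing says that the part on "indirect costs (e.g. time, lost productivity) will be completed at study visits 3, 6 and 12 months". Later in the same section, under the rationale for the EQ-5D, a questionnaire with the same content is said to take "approximately 15 minutes for a subject to complete at baseline and 3, 6 and 12 months".

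Other places that could settle the matter:
- The opening of 3.4.3.f says that resource use is collected during follow-up.
- The baseline list in 5.5.1 "includes UDI, IIQ, EQ5D, Adaptation questionnaire, PGI-I, PGI-S, OAB-q, OAB-sat-q, PISQ". No cost questionnaire is named.
- Table 11 and the matching SAP schedule (4.6) have one row for other patient-reported questionnaires, ticked at the randomisation visit and at 3, 6 and 12 months. The contents of that row are not listed.

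**Models.** Protocol 6.2.3.h plans a generalised linear model for cost (a log link and gamma distribution are given as examples) and ordinary least squares for QALYs. Both contain treatment group, site, the stratification factors and any subject characteristic found to differ significantly between groups. Then comes a term for one model only: "When estimating QALYs, we will also adjust for" baseline utility, because of possible imbalance. No corresponding term is named for cost.

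**SAP.** Section 3.1.3 lists cost-effectiveness as exploratory aim 8. No method follows, and section 11 plans nothing beyond efficacy and safety. Protocol 6.2.3.h is therefore the only specification.

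**The concern.** Two gaps meet here. A site following the first schedule need not give the cost questionnaire before surgery; a site following the second would give it. A baseline that was not taken cannot be recovered afterwards. If it is taken, women spend about 15 minutes on a form whose baseline result has no assured use in the analysis.

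The only route by which baseline cost can enter the cost model is a test of difference between the arms. Under randomisation any such difference is due to chance, so the test does not ask the relevant question. A covariate improves precision because it predicts the outcome, whether or not the arms happen to differ. What is at stake is the width of the interval for the cost difference, which is the numerator of the incremental cost-effectiveness ratio, and through it the bootstrap interval and the acceptability curve.

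**Working it through.** **No figure to reproduce.** The documents state no cost standard deviation, no expected cost difference, no correlation between baseline and follow-up cost, and no power for this aim. The size can only be shown as a range under assumptions.

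**How often the current rule would admit baseline cost.** Protocol 6.2.3.h gives no significance level. If it is the two-sided 0.05 of SAP 7.7 (assumed), a randomised trial admits the covariate with probability about 0.05 and leaves it out with probability 1 - 0.05 = 0.95, however prognostic it is.

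**Precision from always including it.** Write follow-up cost as a questionnaire part plus a medical part (surgery, therapy sessions, complications, additional treatment).
- s = share of total cost variance that comes from the questionnaire part; assumed 0.3 to 0.8.
- rho = correlation of baseline questionnaire cost with follow-up questionnaire cost; assumed 0.2 to 0.6.
- The medical part is taken as unrelated to the questionnaire part and to baseline questionnaire cost.

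The correlation of baseline questionnaire cost with total cost is then rho × sqrt(s). Covariate adjustment multiplies the variance of the cost difference by 1 - s × rho², and its standard error by sqrt(1 - s × rho²).

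| s | rho | s × rho² | Variance falls by | SE ratio | SE falls by |
|---|---|---|---|---|---|
| 0.3 | 0.2 | 0.3 × 0.04 = 0.012 | 1.2% | 0.994 | 0.6% |
| 0.8 | 0.2 | 0.8 × 0.04 = 0.032 | 3.2% | 0.984 | 1.6% |
| 0.5 | 0.4 | 0.5 × 0.16 = 0.080 | 8.0% | 0.959 | 4.1% |
| 0.3 | 0.6 | 0.3 × 0.36 = 0.108 | 10.8% | 0.944 | 5.6% |
| 0.8 | 0.6 | 0.8 × 0.36 = 0.288 | 28.8% | 0.844 | 15.6% |

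At rho = 0 the gain is zero for every s.

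**Check under the planned model type.** The formula is for a linear model, while the protocol's example is a gamma model with log link. A simulation of that model (200 per arm, 600 replicates, baseline acting on the whole cost, so s = 1) compared the spread of the estimated treatment effect with and without the baseline term. The ratio of standard deviations was 0.999 at correlation 0, 0.946 at about 0.27 and 0.811 at about 0.46. The linear formula gives sqrt(1 - 0.27²) = 0.963 and sqrt(1 - 0.46²) = 0.888 for the last two. The simulated gain is somewhat larger, as expected when the covariate is fitted in exactly the form that generated the data. The simulation supports the direction of the effect, not a particular size.

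**The case against.** **The two schedules may be compatible.** The first statement does not say that the follow-up visits are the only ones. It comes in a description of how costs during follow-up are captured, and the questionnaire row of Table 11 fits the fuller schedule. This stands in part: the baseline reading is the more natural one. It still has to be inferred, because neither the list in 5.5.1 nor Table 11 names the instrument.

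**The cost model is not closed to baseline cost.** A reader might infer that the plan never adjusts for it. That goes too far: the rule on significantly differing characteristics could admit it. What is missing is an unconditional, pre-specified term.

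**The two models need not match.** The protocol's reason for adjusting QALYs is imbalance in baseline utility. If QALYs are built from utilities that include the baseline visit, baseline utility is part of the QALY itself. Baseline pad and laundry cost is not part of follow-up cost. This stands: the asymmetry is not an error, and leaving out baseline cost does not bias a randomised comparison. The case for the term is precision alone.

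**The gain may be negligible.** All women are planned to have a sling between baseline and follow-up, so persistence of pad and time costs cannot be presumed. The questionnaire also omits medical costs, so its baseline value is not baseline total cost. Both points stand.

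**A stronger reading about Table 5.** Protocol 3.4.1.c allows additional treatments that include "other procedure-based treatments (posterior tibial nerve stimulation, Botox), and surgical (sling revision, re-placement, sacral neuromodulation", and a continence pessary, while Table 5 has no line for tibial nerve stimulation, Botox, sacral neuromodulation or pessary. A reader might infer that these go unpriced and that the net cost of BPTx is overstated. The documents do not support this. Section 3.4.3.f says that other incontinence treatment is captured and allows other standardised unit costs, and SAP attachment 16.1 codes all four on the Additional Therapy form. The direction is not fixed either. The plan assumes that 30% of control and 20% of BPTx women request additional treatment. If 20% of control requesters and 30% of BPTx requesters had such a procedure (assumed), the rates would be 0.30 × 0.20 = 0.06 and 0.20 × 0.30 = 0.06, with no difference between arms. A higher share among BPTx requesters is conceivable, since Protocol 3.2 expects surgeons to offer BPTx as additional treatment and reminds women that they may decline it.

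**Conclusion.** The point holds as a minor, nearly free improvement. The protocol gives two schedules for the same questionnaire and nothing else in the documents names the baseline administration. The cost model has no pre-specified baseline cost term, and the conditional route is a poor substitute for one.

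The consequence is limited to precision in exploratory aim 8. The primary UDI analysis, the secondary outcomes and the sample size of 472 are unaffected. Under the assumed ranges the standard error of the cost difference falls by about 0.6% to 16%, with about 4% at the middle case (s = 0.5, rho = 0.4). These figures rest wholly on the assumed share and correlation, and on medical cost being unrelated to baseline questionnaire cost. If surgery removes the link between earlier and later costs, the gain is close to zero.

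**What to change.** 1. In Protocol 3.4.3.f, give one schedule in both places: baseline, 3, 6 and 12 months. Name the cost questionnaire in the baseline list in 5.5.1 and in Table 11, and carry it into SAP 4.6. If data collection is already past, state which schedule the sites followed.
2. In 6.2.3.h, add baseline questionnaire cost (non-medical and indirect items) to the cost model as a pre-specified covariate, regardless of any test of imbalance. Describe it as questionnaire cost, not baseline total cost.
3. State how a missing baseline value is handled. The base-case analysis uses women with complete data, so a new covariate could otherwise remove women whose follow-up costs are complete. Filling a missing baseline value without regard to treatment arm avoids this.

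The cost is a few sentences. Where the fuller schedule is already followed, there is no added burden on participants. Where the shorter one was followed, the added burden is one questionnaire of about 15 minutes before surgery.
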